Cleft care generally constitutes only a minor part of the clinical load of the disciplines involved - nursing, plastic surgery, maxillofacial surgery, otolaryngology, speech therapy, audiology, counselling psychology, genetics, orthodontics, dentistry. Cleft surgery is almost completely devoid of a sound evidence base. A review of 25 years of the Cleft Palate-Craniofacial Journal identified only 3 randomised control trials, and none of these involved primary surgery (Roberts et al., 1991).

In the Cochrane Collaboration Controlled Trial Register only two randomised control trials of primary surgery are listed: Two small randomised control trials of primary surgery were conducted by Robertson and Jolleys and published in 1968 and 1974. In the first study a sample was randomised in respect of alveolar bone grafting at the time of lip repair. Follow-up revealed a detrimental effect on facial growth in the grafted group (Robertson and Jolleys, 1968). The second study involved two groups of 20 cases where one group's anterior palate closure was delayed until age 5. No benefit for dentofacial growth was found in delaying hard palate closure (Robertson and Jolleys, 1974). A follow up study when the children were 11 years of age reached the same conclusion (Robertson and Jolleys, 1990).

Marsh et al. (1989) alternated palate repair with or without intravelar veloplasty (IVV) in 51 subjects with a broad range of palatal cleft types. Speech evaluations were made at a two year follow-up. No difference in outcome was detected, but the procedure including IVV required a significantly longer operating time. This negative finding has frequently been challenged in British circles because the trialists' technique for IVV was not considered to be sufficiently radical.

All other available research reports have been retrospective, frequently at case series level. An extensive review of these has been undertaken with the conclusion that comparison between reported outcomes is unreliable because of the invariable presence of bias (Semb and Shaw, 1996). A principal source of bias inevitably, is surgical skill.

There are many controversies that would be appropriate to randomised control trials. For combined clefts of the lip and palate, important points of dispute at present are the surgical sequencing of repair and use or non-use of vomerine flaps in closure of the anterior palate. The principal outcome in relation to these choices is the extent to which the potential for good facial growth can be realised, i.e. unsuccessful surgery causes a disturbance of facial growth associated with progressive disfigurement throughout the childhood and teenage years, usually requiring a major corrective procedure in the late teens (maxillary osteotomy). The quality of initial surgery is also important for speech and language development (Grunwell et al., in press).

Preliminary work

Since 1986 members of the trial consortium have been developing a concerted programme of multidisciplinary intercentre research in cleft lip and palate. These include a comparison of surgical outcome in four Scandinavian centres (Friede et al., 1991; Enemark et al.,1993) and six European centres (Shaw et al.,1992a; Mølsted et al.,1992; Mars et al.,1992; Asher-McDade et al.,1992; Shaw et al., 1992b; Shaw et al.,1992c).

This experience provides compelling stimulus for the establishment of randomised control trials in surgery of clefts, though the professional community involved in cleft care has, in the past, rehearsed many arguments against randomised control trials regarding them as unmanageable or unethical (Berkowitz, 1995; Shaw, 1995). These objections have largely been refuted by the initiation of the first multicentre randomised control trial of secondary cleft surgery in 1992 involving centres in the US, Norway, and the North West of England (Sloan et al., 1996).

The British Association of Plastic Surgeons (Cleft Group) has also declared a strong commitment to participation in randomised control trials of primary surgery and a proposal for a multicentre trial in the UK has received ethical approval in 1996.

The Proposed Study

Null hypothesis

The study will test the null hypothesis that variations in surgical technique and staging are not associated with difference in outcome.

Study design

The study will be conducted as a parallel series of three randomised control trials of primary surgery for complete unilateral cleft lip and palate.

Each team will initially register newly born patients at birth with the study co-ordinator. The patient's name, gender and date of birth will be given.

A full description of the proposed study will be presented to the parents and they will be given written information (Appendix 4).

The team will inform the study co-ordinator before 3 months, whether the child is to be entered into the study or not, along with the consent form or the reason for exclusion.

For children entered into the study, the study co-ordinator will provide an envelope just before the first surgery containing the group allocation for the child. The envelope will be opened on the morning of the surgical operation.

Surgical variations

• Variation A. 'The common arm. Short delay hard palate closure':

Lip and soft palate closure at 3-4 months. Hard palate closure at 12 months.

• Variation B. 'Long delay hard palate closure':

Lip and soft palate closure at 3-4 months (as variation A). Hard palate closure at 36 months.

• Variation C. 'Simultaneous hard and soft palate closure':

Lip closure at 3-4 months. Hard and soft palate closure at 12 months.

• Variation D. 'Early hard palate closure with vomer flap':

Lip closure at 3-4 months combined with a single layer closure of the hard palate using a vomer flap. Soft palate closure at 12 months.

(See appendix 2 for detailed surgical protocols).

Participating Teams

The seven Nordic teams will participate in the trials according to the following scheme. (Two UK teams co-ordinated by Manchester will also participate in Trial 3):

Table 1. Participating teams and surgical variations.

Trial	1	2	3
Teams	Aarhus Copenhagen Gothenburg	Helsinki Linköping Stockholm	Belfast Bergen Manchester Oslo
1 st arm	A	A	A
2 nd arm	В	С	D

Inclusion/exclusion criteria

The trial will include Caucasian infants with non-syndromic complete unilateral cleft lip and palate, who are otherwise healthy. A soft tissue bridge of 5 mm or less will be accepted.

Proposed outcome measures

Outcome measures are speech and language development, dentofacial development, nasolabial appearance, hearing, perioperative complication rate, symptomatic fistulae and operation and hospitalisation time, (Appendix 1, 2 and 3).

Proposed sample size

Sample size calculations have been based on data for equivalent outcomes in the previous multicentre comparisons. We have also used the data from the previous controlled trial of intravelar veloplasty published by Marsh et al., (1989). Detectable differences between groups have been set at a level of sufficient clinical importance to persuade most clinicians that a change in practices would be worthwhile. These have been derived from the levels of difference apparent between the better centres of our previous multicentre studies. We will use dental arch relationship as our principal indicator of dentofacial development as this has been shown to discriminate better than any other measure between groups (Friede et al., 1991, Shaw et al., 1992c). Although the previous measuring instrument was developed for UCLP in the early permanent dentition (Mars et al., 1987), a similar instrument has been validated for 5 year olds (Hathorn et al., 1996; Atack et al., 1997).

Speech Assessment

Using the study by Marsh et al., (1989): The sample size is calculated for changes in the proportion of children falling into the VPC (velopharyngeal competency) * and type I categories compared with those falling into the type II & III categories. A two group continuity corrected χ^2 test with a 0.05 two-sided significance level will have 90% power to detect the difference between a Group 1 proportion of 0.600 and a Group 2 proportion of 0.300 (odds ratio of 0.286) when the sample size in each group is 63.

Dental Arch Relationship

Taking an intermediate difference between the centres of 0.4, a sample size of 66 in each group will have 90% power to detect a difference in means of -0.400 assuming that the common standard deviation is 0.700 using a two group t-test with a 0.05 two-sided significance level.

The largest difference between centres in the six centre study was 0.87 (Shaw et al., 1992c, Table 1.9).

Using the GOAL yardstick (Friede et al., 1991, Fig. 4), to detect a 30% difference between two groups for the proportion of cases rated 1 or 2 of 65 per group would be required (with alpha=0.05, beta=0.10).

^{*} VPC (velopharyngeal competency) comprises VPI (velopharyngeal insufficiency) WNL (within normal limits)

Naso-labial appearance

The proposed sample for determining this outcome is based on the overall appearance of the upper lip (L1 in Morrant and Shaw, (1996)). The mean and standard deviation for English patients were used. A sample size of 55 in each group will have 90% power to detect a difference in means of 0.320 (the difference between a Group 1 mean of 2.720 and a Group 2 mean, of 2.400), assuming that the common standard deviation is 0.510 using a two group t-test with a 0.05 two-sided significance level.

If the vermilion border from Table 1 of Asher-McDade et al., (1992) is used as the outcome, a sample size of 60 in each group will have 90% power to detect a difference in means of -0.300 (the difference between a Group 1 mean, of 2.800 and a Group 2 mean, of 3.100) assuming that the common standard deviation is 0.500 using a two group t-test with a 0.05 two-sided significance level.

Using the data from Enemark et al., (1993, Table 3) the mean basal view for centre D was 2.26 (SD=1.11), assuming that the mean difference between the measurements was 0.70 (SD=1.11), then a sample size of 65 per group would be required (with alpha=0.05, beta=0.10).

Ethical approval

A full description of the proposed study will be presented to parents and they will be given written information (Appendix 1). Each team will seek ethical approval from the appropriate authorities.

Planned recruitment rate

The above estimates indicate that we will need minimum group sizes between 55 and 66 subjects per group. We propose to recruit 75 cases to each group to compensate for potential drop-out.

On the basis of the present annual numbers of patients born with UCLP, table 2 demonstrates likely recruitment rate:

Trial	1	2	3
Teams	Aarhus Copenhagen Gothenburg	Helsinki Linköping Stockholm	Belfast Bergen Manchester Oslo
New UCLP cases per year	40	31	65
Period required for sample of 150 cases per trial	3.75 years	4.8 years	2.31

Table 2. Recruitment Rates

Randomisation

Random assignment will be in sealed envelopes which will be given to each team and kept in the operating theatre, and should be opened just prior to surgery.

Proposed frequency/duration of follow-up

Existing patterns and traditions of follow-up at respective teams will not be interfered with. The additional records agreed upon for judgement of outcomes are listed in Appendix 3 and 4. The proposed 60 month period of the project will allow definite conclusions to be reached on perioperative complications and their costs, direct surgical costs, speech and audiological outcome, scar healing, the size of the residual hard palate cleft prior to closure and nasolabial appearance. The first attempt to measure dentofacial growth outcome will be carried out on study casts and cephalograms obtained at age 5 years.

Measurements of outcome and statistical analysis

Analysis of the records will be performed by blinded panels using standardised rating schemes. Repeatability tests will be performed. Appropriate multiple comparison tests will be performed.

Publications and presentations

A minimum of one member from each team will be on every publication. Each team will decide who has done most of the work and determine authorship. The first author should be the person doing most of the work.

References

Berkowitz S. Ethical issues in the case of surgical repair of cleft palate. Cleft Palate-Craniofac J 1995; 32: 272-276.

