The lip and soft palate will be closed at 3-4 months. The hard palate will be closed at 12 months.

Lip closure:

The technique for lip closure that is presently used in the respective teams will be performed. For description, see Variation B, C and D.

Posterior palatoplasty with a posteriorly based vomer flap

Drawing

A line is drawn in a zig-zag fashion along the border between the hard and the soft palate. Start in the hamulus region and from there anteriorly to the tuber. The line is then continuing in a medial-anterior direction for about 5 mm and then 90 degrees medial-posteriorly for another 5 mm, from there turning medial-anteriorly again and 1 cm lateral to the cleft border, creating a triangular mucoperiosteal flap in the medial part of the hard palate.

The triangular vomer flap is drawn posteriorly based as wide and long as needed to cover the defect in the nasal mucosa. (The flap is planned to reach about 5mm posterior to the vomero-premaxillary suture, Picture series 1, Fig. 1).

Local anaesthesia

Local anaesthesia with adrenaline is used in the soft and hard palate and in the vomer.

Incisions

Starting laterally, the mucosa is incised superficially along the drawn lines. Medial to the palatine vessel, the incision is going deeper down to the bone. The vomer flap is raised subperiostally as shown in the drawing. At the cleft border in the soft palate, an incision is made along the border between the nasal and oral mucosa, dividing the soft palate into two layers (Picture series 1, Fig. 2. V= vomer flap, L= lateral flaps with mucoperiost in their anterior part from the hard palate).

Dissection

The oral mucosa is dissected subperiostally in the anterior part from the hard palate. The incision above hamulus is deepened by blunt dissection and the hamulus is identified, but

not broken (Picture series 1, Fig. 3. V = vomerflap, H = hamulus). Using blunt and sharp dissection, the oral mucosa of the soft palate is mobilised posteriorly. A tunnel is made by blunt dissection from the hamulus, going medially at the border of the hard palate to the incision of the cleft edge (Picture series 1, Fig.4).

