From this point the distance measuring half a Cupid's bow is kept in a pair of callipers and is set off along the planned future philtrum ridge. From the calculated point of the Cupid's bow nearest to the cleft on the medial side an incision line is made along the vermilion border closest to the cleft, where the white skin roll can still be identified. From this point an incision line, measuring half a Cupid's bow is marked anteriorly to the muscle bulge on the lip on the cleft side. At the cranial endpoint of this line, the same distance is marked laterally at a right angle (90°). Incisions are then made along the planned lines through the whole lip. The medial lip frenulum is trimmed and the sulcus line is brought up to the same depth as on the non cleft stage, but the alar wing often needs further mobilisation between the cartilage and the skin. Subdermal dissection over the alar cartilages is performed ad modum McComb. Any excessive lip and scar tissue in the cleft area is then excised or used for augmentation of the columella base on the cleft side. The lip is approximated and sutured on the oral side. In the next step the musculature is closed where the incision, following the incision line 90° to the incision from the vermilion, is dividing the musculature in the lip into two parts, one downwards, representing the orbicularis oris muscle, and one upwards, representing muscles coming from the zygomatic and nasal musculature. These muscles are sutured separately where the upper part brings the alar wing into position and the lower part is reconstructing the freely moving orbicularis oris muscle. The skin can then be sutured without tension, and sutures tied over cotton wool bolsters according to McComb are placed through the alar wing on the cleft side to lift the cartilage in the dome area, stabilise the position and to prevent haematoma. Finally, the nostrils are packed with gauze.

Posterior palatoplasty:

Posterior palatoplasty with a posteriorly based vomer flap will be performed together with lip closure as described on page 9-10.

Hard palate closure:

Closing of the residual cleft in the hard palate will be done at 36 months. The technique used will be identical to the one described on page 11.

Variation C: Simultaneous hard and soft palate closure.

Timing of surgery:

The lip will be closed at 3-4 months. The hard and soft palate will be closed at 12 months.

Lip closure techniques:

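### Trial 1 opens the allocation before a first operation that is the same in both arms, so that operation is done unblinded for no stated reason

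*Protocol*

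**What the plan says.** The enrolment text of the Protocol (The Proposed Study, before the list of surgical variations) states that "the study co-ordinator will provide an envelope just before the first surgery containing the group allocation for the child", and then that "The envelope will be opened on the morning of the surgical operation". The Randomisation section says that the envelopes are "kept in the operating theatre, and should be opened just prior to surgery". The two places differ on who holds the envelope, but both have it opened before the operation, and neither makes an exception for any trial.

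Table 1 assigns variations A and B to Trial 1 ("Aarhus Copenhagen Gothenburg"). Under Surgical variations, A is "Lip and soft palate closure at 3-4 months. Hard palate closure at 12 months" and B is "Lip and soft palate closure at 3-4 months (as variation A). Hard palate closure at 36 months".

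Appendix 2 gives the same picture. Variation A uses whatever lip repair the team already practises. Variation B's soft palate repair refers back to the description under A. On B's later hard palate closure, Appendix 2 says: "The technique used will be identical to the one described on page 11".

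The only blinding described is in the section on measurement and analysis, where the records are rated by panels that do not know the arm.

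**The concern.** Trial 1 asks what the age at hard palate closure does. Everything before that closure is meant to be common to the arms. If the surgeon knows during the first operation whether the remaining cleft will stay open until 12 or 36 months, the shared repair may be done differently in the two arms, even without intent. Any such difference would be read as an effect of timing.

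The first operation feeds outcomes that the protocol lists: complications, time in theatre and in hospital, nasolabial appearance, and the size of the hard palate cleft that remains before closure. It also includes the soft palate and muscle repair, so it bears on velopharyngeal competence, the basis of the speech sample size. Panels that rate later records cannot remove a difference made at surgery. Operating time, blood loss and early complications are entered on a surgical form that also carries the arm.

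**Working it through.** No power or sample-size figure enters this point. The check compares the two arms of Trial 1 at each step and sets the result against the moment the envelope is opened.

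| Step | Arm A | Arm B | Same? |
|---|---|---|---|
| Lip repair, 3-4 months | team's own technique | technique described under B | yes, within a Trial 1 team |
| Soft palate repair, 3-4 months | posterior palatoplasty, Appendix 2 | refers back to A | yes |
| Hard palate technique | Appendix 2, Variation A | stated to be identical | yes |
| Age at hard palate closure | 12 months | 36 months | **no** |

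**Time from opening to first divergence, Trial 1.** The envelope is opened at 3-4 months and the arms first differ at 12 months: 12 − 4 = 8 months to 12 − 3 = 9 months.

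**Trials 2 and 3.** Arm A closes the lip and soft palate at the first operation. C closes the lip only. D closes the lip and the hard palate with a vomer flap. The arms differ at that operation, so the gap is 0 months and opening beforehand is unavoidable.

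**Children affected.** 75 per group × 2 groups = 150 planned in Trial 1, each for one of two staged operations.

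**Room for judgement in the shared operation.** Appendix 2, Variation A, says: "The triangular vomer flap is drawn posteriorly based as wide and long as needed to cover the defect in the nasal mucosa". It also anchors the oral edges only if they are mobile, and asks the surgeon to describe how the muscle was reconstructed. The discretion has limits: the flap has an anatomical landmark about 5 mm from a named suture line, and it is sewn into the nasal layer over about 10 mm.

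**The case against.** The case for leaving the rule alone has four parts.

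- **The operation is tightly described.** Flap size is tied to the defect and to a landmark, and the surgical form has a field for departures from the described technique. This stands: it limits the scope for bias but does not remove it. No direction of bias can be argued from the text.
- **A reason may exist.** One opening rule across parallel trials with a common arm is simple to run, and the null hypothesis covers staging as well as technique. This is plausible, but the protocol does not say it. The fair statement is that no reason is given, not that none exists.
- **The second operation cannot be blinded anyway.** True. Only the first stage can be protected.
- **Allocation is concealed until the day of surgery.** Also true. A reader might infer that concealment fails or that the protocol contradicts itself here. Neither follows: the issue is knowledge of the arm during surgery, not foreknowledge at enrolment.

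A reader might also be tempted to go further and release the allocation only at the 12-month visit, expecting to save drop-out allowance and gain a baseline speech measure. The documents do not support that.

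- Arm A's own hard palate surgery falls at 12 months, which leaves little time to book it. Moving randomisation itself that late would also let families withdraw selectively after seeing the first repair.
- Early losses would be moved, not avoided. Table 2 already counts every new case (40 per year × 3.75 years = 150), and no loss rate before 12 months is given. The allowance is not one figure either: 1 − 66/75 = 12% for dental arch relationship, 1 − 63/75 = 16% for speech, and 1 − 55/75 = 27% for lip appearance.
- The 12-month speech observation is already made before that surgery, and the protocol says it is not used for the main outcome. Any use as a covariate is optional.

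**Conclusion.** The point holds for Trial 1 only. The protocol reveals the arm 8 to 9 months before it affects care, so that one shared operation in each of 150 planned children is done with the arm known, and no reason is stated. This is an avoidable route for performance bias into listed outcomes. It is not evidence that bias occurred, and its size is unknown. The 8 to 9 months is elapsed time; the exposure that matters is the single first operation and the recording of it.

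The conclusion assumes that each Trial 1 team uses one lip technique in both arms, as Appendix 2 indicates, and that no separate Trial 1 instruction, not shown here, already delays the opening.

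**What to change.** Add a Trial 1 sentence to both the enrolment text and the Randomisation section. It should say that the envelope is assigned to the child at the first operation as now, stays sealed until that operation and its operative record are complete, and is then opened in time to schedule the second operation. Because the child is still allocated at the first operation, losses between the two operations stay in the randomised comparison.

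The arm box on the surgical form should be left blank for Trial 1 until the envelope is opened. If nights in hospital are also to be recorded without knowledge of the arm, the opening can wait until discharge.

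Trials 2 and 3, the sample size and the surgical schedules do not change. The cost is a separate opening rule for one trial, with families and theatre planners learning the arm slightly later.
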